Social support messages are an important part of close relationships (Cutrona & Suhr, 1992); however, recipients perceive some supportive messages to be unhelpful or unwanted (Floyd & Ray, 2017). In general, emotional support messages are viewed as a particularly useful form of support in the months following a cancer diagnosis (Arora et al., 2007). There are instances, though, of cancer patients viewing some emotional support messages negatively (Ray & Veluscek, 2017, 2018). Much of the prior research looking at peoples' reactions to emotional support messages have done so by looking for differences between high, moderate, and low-quality messages (High & Dillard, 2012), and have not considered the possibility that some offers of emotional support may contain both positive statements of empathy and caring and also negative statements of criticism and blame. Therefore, the present study investigates how cancer patients rate emotional support messages that consist of different percentages of positive and negative statements. Additionally, prior research has shown that some messages may be retained in memory for years after they are communicated (Knapp, Stohl, & Reardon, 1981), and some of these memorable messages can be classified as supportive messages (Wang, 2012). However, minimal research has focused on what is specifically remembered from supportive messages, particularly if those messages are composed of both positive and negative statements. Research by Ray and Veluscek (2017) has shown, though, that cancer patients can readily recall both positive and negative support messages received in the year after initial diagnosis and that receiving negative messages sometimes led to re-evaluating whether future updates would be shared with the supporter. Furthermore, the well-supported propensity for humans to pay greater attention and give more processing to negative information than positive information (Baumeister, 2001), would suggest that negative portions of ambivalent support messages would have a stronger influence on the recipient, particularly in terms of what is recalled (Bless, Hamilton, & Mackie, 1992; Finkenauer & Rimé, 1998). The present study tests this negativity bias and the findings will illuminate how cancer patients process, perceive, and recall emotional support messages that have both positive and negative components. To test the possible effects of negative portions of messages, 18 message conditions have been developed (see list provided under Participation heading). This results in a nested factorial design in which you have 5

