
message conditions (0, 20, 40, 60, or 80 percent negativity), 2 conditions based on the placement of the negative portions (beginning or end), and 2 versions of each message condition to allow for the messages to be analyzed as random factors. A 5x2x2 design typically yields 20 cells; however, when there is 0% negative portions of a message, it is unnecessary to consider the placement of the negative portions that do not exist. This results in 18 conditions as opposed to 20 conditions.

Study Purpose/Objective

To understand how cancer patients react to and recall emotional support messages that contain different percentages of positive statements of empathy and caring and also negative statements of criticism and blame.

Study Aims

Aim #1: To determine how cancer patients rate emotional support messages that consist of differing percentages of negative statements (0, 20, 40, 60, or 80 percent) and messages in which those negative portions occur at either the beginning or end of the supportive message.

Aim #2: To determine what portions of emotional support messages that consist of differing percentages of negative and positive statements cancer patients recall in the minutes after reading a message, and whether the placement of the negative portions at either the beginning or end of the message also affects recall.

Hypotheses & Research Questions

Hypotheses 1-4 and Research Questions 1-4 address Study Aim #1.

H1: Cancer patients' ratings of message effectiveness differ based on the percentage of the support message that is negative.

RQ1: How, if at all, do cancer patients' ratings of message effectiveness differ depending on whether negative portions of messages occur at the beginning or end of the entire message?

H2: Cancer patients' ratings of supporter competence differ based on the percentage of the support message that is negative.

RQ2: How, if at all, do cancer patients' ratings of supporter competence differ depending on whether negative portions of messages occur at the beginning or end of the entire message?

H3: Cancer patients' likelihood of seeking support from a supporter in the future differs based on the percentage of the support message that is negative.

RQ3: How, if at all, do cancer patients' likelihood of seeking support from a supporter in the future differ depending on whether negative portions of messages occur at the beginning or end of the entire message?

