H4: Cancer patients' self-reports of emotional improvement after receiving a support message differs based on the percentage of the support message that is negative.

RQ4: How, if at all, do cancer patients' self-reports of emotional improvement after receiving a support message differ depending on whether negative portions of messages occur at the beginning or end of the entire message?

Hypotheses 5-7 address Study Aim #2.

H5: Cancer patients recall negative portions of supportive messages more frequently than they recall positive portions of supportive messages.

H6: As the percentage of negative portions of a supportive message increases, cancer patients likelihood to recall negative portions of supportive messages also increases.

H7: The number of negative words recalled from the supportive messages by cancer patients differ depending on the percentage of the message that is negative.

Methods

This is a cross-sectional, observational survey study. Data will be collected through a mass email disseminated through the online survey platform Qualtrics.

Recruitment and Eligibility

800 participants will be recruited from Moffitt TCC-consented patients who have agreed to be contacted for future research.

Inclusion Criteria: Living patients, 18 years of age or older, diagnosis of breast, prostate, thoracic, or digestive cancer in the past 3 years, consent to the Moffitt TCC protocol and indication of their willingness to be contacted for future research by including an email contact, and ability to read and write fluently in English.

A random selection of at least 800 patients who fit inclusion criteria will be drawn by Moffitt Collaborative Data Services. An invitation to participate in the current study will be sent to participants via an email disseminated through the online survey host Qualtrics. The contact list of email recipients will be uploaded into the Qualtrics system and the email will be sent from [name] (study team member). If a potential participant were to choose to reply to this email with questions about the study or for any other reason, these replies would be sent to [name], who would be tasked with responding to the potential participant's message. The invitation will include a description of the study and a link to the study survey.

Consent Process

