Statistical analyses will consist of 5x2x2 nested factorial ANOVA models. The first study aim will be tested through 4 ANOVA models that will test for differences between participants who received the different messages in terms of 1) perceived message effectiveness, 2) perceptions of supporter competence, 3) likelihood to seek support from the supporter in the future, and 4) self-reports of emotional improvement. Depending on the correlations among the dependent variables, a MANOVA may be used instead of an ANOVA to test the first aim of the study. Similarly, if significant covariates (such as age or times since diagnosis) are found, the ANOVA/MANOVA could become an ANCOVA or MANCOVA. To test the second aim of the study, a chi-square analysis will test to see if participants recall negative portions of messages more frequently than positive portions of messages depending on which message they received (i.e., dependent on the position and percentage of the negative message portions). The second aim will also be tested using ANOVA models to determine if significant differences occurred in the number of negative words that were recalled across the 18 messages received (i.e., dependent on the position and percentage of the negative message portions). The software program LIWC (Linguistic Inquiry and Word Count) will be used determine the number of negative words recalled by the participants in their open-ended responses.

Potential Benefits

There are no benefits for being in this study; however, by joining this research study, the participant is helping to provide information which may help science and society.

Potential Risks

Because of the personal nature of the questions to be asked, the participant might reflect on unpleasant memories while completing the questionnaire. Although not expected to occur, it is

possible that a breach of confidentiality could occur if the computer on which the data file is stored is compromised or otherwise hacked or illegally accessed.

Compensation, Benefits, and Risks

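### The Aim 2 recall analyses ignore how much negative and positive text each message shows, so H6/H7 percentage effects are not evidence of negativity bias and H5 misleads if read by condition or with the 0% messages included

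*Combined protocol and SAP*

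**What the plan says.** The background of the combined protocol and SAP argues that "negative portions of ambivalent support messages would have a stronger influence on the recipient, particularly in terms of what is recalled" and then states: "The present study tests this negativity bias". Aim 2 and H5 to H7 carry the recall question.

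- **Hypotheses & Research Questions.** "H5: Cancer patients recall negative portions of supportive messages more frequently than they recall positive portions of supportive messages". The next begins "H6: As the percentage of negative portions of a supportive message increases" and predicts that recall of negative portions becomes more likely. H7 says that the count of negative words recalled differs by percentage. None of the three gives a denominator.
- **Participation and the background's design paragraph.** All 18 messages have 100 words, with 0, 20, 40, 60 or 80% negative, placed first or last. There are "2 versions of each message condition to allow for the messages to be analyzed as random factors".
- **Planned Analyses.** The general model is stated as "Statistical analyses will consist of 5x2x2 nested factorial ANOVA models". For Aim 2, a chi-square tests whether participants "recall negative portions of messages more frequently than positive portions of messages depending on which message they received", and an ANOVA tests whether "significant differences occurred in the number of negative words that were recalled across the 18 messages received". The count comes from LIWC applied to the free-text answers.

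No section gives a proportion, an offset, an expected share based on the text shown, or a rule for leaving out the 0% messages.

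**The concern.** Total length is fixed, so the manipulated percentage is also the amount of negative text available to recall, and positive text falls by the same amount. A reader who remembers both kinds equally well will return more negative material from an 80% message than from a 20% message. Two errors could follow.

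- A significant H6 or H7 percentage effect could be reported as support for negativity bias, when it is what one expects without any bias.
- H5 is the contrast that speaks to bias. Read message by message, as the chi-square is described, it could hide or reverse a real bias at low percentages and exaggerate or create one at high percentages.

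The claim to have tested bias in recall would then rest on analyses that do not isolate it.

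**Working it through.** **The plan's own figure.** With f = 0.25, alpha 0.05, 18 groups and power 0.95, the noncentrality is 0.25² × 479 = 29.9 on 17 and 461 df. Power is 0.9502, so the stated 479 is reproduced. It is used below only as a sample size.

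**Expected shares.** Let p be the negative fraction of the message (from the documents) and b the per-word recall rate of negative text relative to positive text (b = 1 is no bias). The negative share of recalled text is bp / (bp + 1 − p). It exceeds one half only if b > (1 − p)/p.

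| Negative text | Words shown, neg:pos | Share, b = 1 | Share, b = 2 | b needed for a share above 50% |
|---|---|---|---|---|
| 20% | 20:80 | 20% | 0.4/1.2 = 33% | 4.0 |
| 40% | 40:60 | 40% | 0.8/1.4 = 57% | 1.5 |
| 60% | 60:40 | 60% | 1.2/1.6 = 75% | 0.67 |
| 80% | 80:20 | 80% | 1.6/1.8 = 89% | 0.25 |

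With no bias, expected recall of negative-portion text rises fourfold from 20% to 80% and is zero at 0%. A true twofold bias looks reversed at 20%. A true halving of negative recall (b = 0.5) looks like negativity bias at 80%: 0.4/0.6 = 67%.

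**Pooling.** There are two 0% messages and four at each other level. Negative words shown: 4 × (20 + 40 + 60 + 80) = 800. Positive words: 800 in the 16 mixed messages, plus 200 in the two 0% messages.

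- All 18 messages: 800/1800 = 44.4% negative.
- The 16 mixed messages: 800/1600 = 50%.

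**Position.** A 20%-first message and an 80%-last message are split at the same word with the labels swapped; the same holds for every other pair. Equal weight over the eight conditions therefore cancels any start, middle or end advantage. It does not cancel at one percentage. If both ends are recalled 2.5 times as well as the middle (assumed), the no-bias difference in recall per word, negative minus positive, relative to average, is +0.40, +0.13, −0.13 and −0.40 at 20, 40, 60 and 80%, which sums to zero.

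**Simulation of H5 at N = 479.** The documents give no recall rate, so these are ranges over assumptions: phrases of 5, 10 or 20 words, 5, 15 or 30% recalled, between-person correlation 0 or 0.2. Any negative recall is compared with any positive recall by exact McNemar test.

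- By level, no bias (479 × 4/18, about 106 people each): significant toward positive in 73-100% of runs at 20% and 6-61% at 40%; toward negative in 11-62% at 60% and 71-100% at 80%. Separately coded repeats moved the lower ends to between 71 and 76% at 20% and between 69 and 80% at 80%.
- By level, true recall odds ratio of 2 favouring negative text: the 20% messages still point significantly to positive in 30-99% of runs (median 83%).
- Pooled over all 18 messages, no bias: significant toward positive in 16-100%.
- Pooled over the 16 mixed messages: 0-6% rejection with no bias; 73-100% power at an odds ratio of 2. These pooled runs assume no difference in memorability between messages.

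**H6 and H7.** The direction follows from the text shown; how often it reaches significance depends on coding. At N = 479 over 20-80% with no bias, H6 rejects in anything from 12 to 100% of runs. It is low where nearly everyone recalls some negative text or people differ greatly. For H7 the corresponding range is 17-100%. That is a proxy: it counts all words of the negative portion, not the planned LIWC count.

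**The case against.** The strongest reply has three parts.

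1. **H5 names no condition.** Compared overall in the mixed messages with equal weight, exposure is balanced exactly, so an unscaled within-person test is sound. This stands. A reader might infer that lack of scaling defeats H5 altogether; the design does not support that. What remains is that Planned Analyses describes the comparison as varying by message received and excludes no condition, so neither the equal-weight pooling nor the omission of the 0% messages is in the plan.
2. **H6 and H7 are answerable as worded.** This also stands. H6 predicts a rise and H7 a difference, and the planned tests address those statements. A reader might infer that the tests are invalid; they are not. The difficulty is only in treating their result as bias, which the background invites by presenting the study as a test of it.
3. **LIWC scores words, not portions.** A positive statement may contain words scored as negative. The zero at 0% and the exact fourfold rise therefore hold for negative-portion text, not necessarily for the LIWC count. That count should still rise with the amount of negative text, but the documents supply no LIWC rates.

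The simulated rates also rest on assumed recall behaviour and are wide. The expected shares and the pooling balance are arithmetic from the design, given equal recall per word.

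**Conclusion.** The concern holds for how Aim 2 may be analysed and interpreted. The no-bias negative share is 20, 40, 60 and 80% by condition, so a percentage effect in H6 or H7 is expected from exposure alone. By-condition H5 results judged against an even split change direction between 40% and 60%. Including the 0% messages moves the pooled no-bias share to 44.4%, which can hide a bias.

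These figures need only the stated message composition and equal per-word recall as the definition of no bias. Rejection rates need further assumptions and serve as illustration.

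First-versus-last contrasts at the same percentage show equal amounts of negative text and are not affected by this exposure difference; neither is Aim 1. The point should be settled before recall is coded.

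**What to change.** 1. Name H5 as the test of negativity bias. Compare negative with positive recall within person in the 20-80% messages only, with equal weight over the eight percentage-by-placement conditions and message as a random factor, as the design paragraph intends. The message-level error term matters: if messages differ in memorability (assumed log-odds SD 0.3), a participant-level paired t-test on recall proportions rejects in 7-31% of no-bias runs, against 3-8% with the message-level term.
2. Preferably score the proportion of the assigned message's negative text recalled and the proportion of its positive text recalled, by a rule written in advance. Any condition-level H5 result should be scaled this way or compared with 20, 40, 60 or 80%, not 50%, with a note that position effects do not cancel at a single percentage.
3. Keep H6 and H7 as worded, and state that a percentage effect reflects the amount of negative text shown and is not evidence of bias. Leave the 0% messages out of H6, where negative-portion recall is zero by construction. Keeping them in a LIWC-based H7 is optional.

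**Cost.** Free-text answers must be matched to the assigned message, and paraphrases make this real coding work. The H5 test loses 2/18 = 11% of participants (about 53 of 479, or 89 of 800). The message-level error term costs power: at N = 479 the scaled H5 test has 73-100% power for a true odds ratio of 2 and 34-100% (median 92%) for 1.5. If messages differ as assumed above, the figures are 68-100% and 25-85% (median 66%). The plan's 0.95 target was set for a different test. Messages and questionnaire need no change.
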